## 10.7. Appendix 7: Values of Potential Clinical Importance

## 10.7.1. ECG

ECG Parameter	Units	Potential Clinically	Potential Clinically Important Range		
		Lower	Upper		
Absolute					
Absolute QTc Interval	msec	<320	>450		
Absolute PR Interval	msec	< 120	> 200		
Absolute QRS Interval	msec	< 60	> 120		
Change from Baseline					
Increase from Baseline QTc	msec		> 60		

## 10.7.2. Vital Signs

Vital Sign Parameter	Units	Potential Clinically Important Range		
(Absolute)		Lower	Upper	
Systolic Blood Pressure	mmHg	< 85	> 140	
Diastolic Blood Pressure	mmHg	< 45	> 90	
Heart Rate	bpm	< 40	> 100	

## 10.8. Appendix 8: Abbreviations & Trade Marks

## 10.8.1. Abbreviations

Abbreviation	Description
ADaM	Analysis Data Model
AE	Adverse Event
AUC	Area under the Plasma Concentration-Time Curve
AUC(0-τ)	AUC from Time 0 to the End of the Dosing Interval at Steady State
CDISC	Clinical Data Interchange Standards Consortium
CI	Confidence Interval
Cmax	Maximum Observed Concentration
C-SSRS	Columbia Suicide Severity Rating Scale
Cτ	Plasma Concentration at the End of the Dosing Interval
CV b	Coefficient of Variation (Between)
DBF	Database Freeze
DBR	Database Release
DP	Decimal Places
ECG	Electrocardiogram
eCRF	Electronic Case Record Form
FTC	Emtricitabine
GSK	GlaxoSmithKline
HIV	human immunodeficiency virus
ICH	International Conference on Harmonization
IDSL	Integrated Data Standards Library
LLN	Lower Limit of Normal
PK	Pharmacokinetic
QD	Once Daily
RAP	Reporting & Analysis Plan
SAC	Statistical Analysis Complete
SAE	Serious Adverse Event
SD	Standard Deviation
SDTM	Study Data Tabulation Model
TAF	Tenofovir Alafenamide
TFV	Tenofovir
Tmax	Time of Maximum Observed Concentration
ULN	Upper Limit of Normal

## 10.8.2. Trademarks

Trademarks of the GlaxoSmithKline Group of Companies	
NONE	

Trademarks not owned by the GlaxoSmithKline Group of Companies	6
SAS	
WinNonlin	

## 10.9. Appendix 9: List of Data Displays

## 10.9.1. Data Display Numbering

The following numbering will be applied for RAP generated displays:

Section	Tables	Figures	
Study Population	1.1 to 1.7		
Safety	2.1 to 2.19	2.1	
Pharmacokinetic	3.1 to 3.19	3.1 to 3.20	
Section	Listings		
ICH Listings	1 to 30		
Other Listings	31 to 37		

## 10.9.2. Mock Example Shell Referencing

Non-IDSL specifications will be referenced as indicated and if required example mock-up displays provided in the Table/Listing/Figure Shells.

Section	Figure	Table	Listing
Study Population	POP_Fn	POP_Tn	POP_Ln
Safety	SAFE_Fn	SAFE_Tn	SAFE_Ln
Pharmacokinetic	PK_Fn	PK_Tn	PK_Ln

#### NOTES:

• Non-Standard displays are indicated in the 'IDSL / Example Shell' or 'Programming Notes' column as '[Non-Standard] + Reference.'

#### 10.9.3. Deliverables

Delivery	Description
SAC	Final Statistical Analysis Complete

## 10.9.4. Study Population Tables

Study	Study Population Tables						
No.	Population	IDSL / Example Shell	Title	Programming Notes	Deliverable [Priority]		
Subjec	t Disposition						
1.1.	Safety	NS1	Summary of Number of Subjects Enrolled by Country and Site ID		SAC		
1.2.	Safety	ES1A	Summary of Subject Disposition for the Subject Conclusion Record		SAC		
1.3.	Screened	SD1	Summary of Screening Status and Reasons for Screen Failures		SAC		
Protoc	ol Deviation						
1.4.	Safety	DV1	Summary of Important Protocol Deviations		SAC		
Demog	raphic and Bas	eline Characteris	tics				
1.5.	Safety	DM3	Summary of Demographic Characteristics		SAC		
1.6.	Safety	DM5	Summary of Race and Racial Combinations		SAC		
1.7.	Safety	DM11	Summary of Age Ranges		SAC		

## 10.9.5. Safety Tables

Safety:	Tables				
No.	Population	IDSL / Example Shell	Title	Programming Notes	Deliverable [Priority]
Advers	e Events (AEs)			•	
2.1.	Safety	AE1CP	Summary of Adverse Events by System Organ Class and Preferred Term		SAC
2.2.	Safety	AE1CP	Summary of Drug-Related Adverse Events by System Organ Class and Preferred Term		SAC
2.3.	Safety	AE3	Summary of Common (>=5%) Adverse Events by Overall Frequency		SAC
2.4.	Safety	AE15	Summary of Common (>=5%) Non-serious Adverse Events by System Organ Class and Preferred Term (Number of Subjects and Occurrences)		SAC
2.5.	Safety	AE16	Summary of Serious Adverse Events by System Organ Class and Preferred Term (Number of Subjects and Occurrences)		SAC
2.6.	Safety	AE5A	Summary of Adverse Events by System Organ Class and Preferred Term and Maximum Intensity		SAC
Labora	tory: Chemistry	/			•
2.7.	Safety	LB1	Summary of Clinical Chemistry Changes from Baseline		SAC
2.8.	Safety	LB16	Summary of Clinical Chemistry Results by Maximum Grade Increase Post-Baseline Relative to Baseline		SAC
Labora	tory: Hematolo	gy		•	
2.9.	Safety	LB1	Summary of Hematology Changes from Baseline		SAC
2.10.	Safety	LB16	Summary of Hematology Results by Maximum Grade Increase Post-Baseline Relative to Baseline		SAC

Safety: Tables						
No.	Population	IDSL / Example Shell	Title	Programming Notes	Deliverable [Priority]	
Labora	tory: Urinalysis	,				
2.11.	Safety	UR3	Summary of Urinalysis Dipstick Results		SAC	
2.12.	Safety	LB1	Summary of Urine Concentration Changes from Baseline		SAC	
2.13.	Safety	LB16	Summary of Urinalysis by Maximum Grade Increase Post- Baseline Relative to Baseline		SAC	
ECG						
2.14.	Safety	EG1	Summary of ECG Findings		SAC	
2.15.	Safety	EG2	Summary of ECG Changes from Baseline		SAC	
2.16.	Safety	EG10	Summary of Maximum QTc Values Post-Baseline Relative to Baseline by Category		SAC	
2.17.	Safety	EG11	Summary of Maximum Increase in QTc Values Post-Baseline Relative to Baseline by Category		SAC	
Vital Si	gns					
2.18.	Safety	VS1	Summary of Vital Sign Changes from Baseline		SAC	
C-SSR	S					
2.19.	Safety	CSSRS4	Listing of C-SSRS Suicidal Ideation and Behavior Data	Only include participants who have suicidal ideation or behavior	SAC	

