# 3. OBJECTIVES AND ENDPOINTS

Objective	Endpoint

 
Primary
 
To assess the effect of GSK3640254 on the PK of TAF, FTC, and the active metabolite of TAF prodrug, TFV under fed conditions in healthy participants
 
	
 
AUC(0-τ) and Cmax for TAF
 
AUC(0-τ), Cmax, and Cτ for FTC and TFV
 

 
Secondary
 
To assess the safety and tolerability of
 
	
 
Safety and tolerability parameters for
 

TAF/FTC administered alone and when coadministered with GSK3640254 in healthy participants	AEs/SAEs, observed and change from baseline clinical laboratory assessments, ECGs, and vital sign measurements
• To characterize the steady-state PK of GSK3640254 in the presence of TAF/FTC in healthy participants	
 
AUC(0-τ), Cmax, Cτ, and Tmax for GSK3640254
 

• To characterize the steady-state PK of TAF, FTC, and TFV alone and in combination with GSK3640254 in healthy participants	
 
Tmax for TAF, FTC, and TFV
 

AE = adverse event; AUC  $(0-\tau)$  = area under the plasma concentration-time curve from time 0 to the end of the dosing interval at steady state; Cmax = maximum observed concentration; C $\tau$  = Plasma concentration at the end of the dosing interval; ECG = electrocardiogram; FTC = emtricitabine; PK = pharmacokinetics; SAE = serious adverse event; TAF = tenofovir alafenamide; TFV = tenofovir; Tmax = time of maximum observed concentration.

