# 4. STUDY DESIGN

# 4.1. Overall Design

This is a Phase 1, open-label, fixed-sequence 2-period, one-way drug interaction study designed to assess the PK, safety, and tolerability of GSK3640254 and TAF/FTC when administered alone and in combination in healthy participants.

The study will consist of a screening period and 2 sequential treatment periods. Participants will be screened within 28 days before the first dose of study intervention. The treatments will be as follows:

- Treatment A: TAF/FTC 25/200 mg QD on Days 1 through 14 (Period 1)
- Treatment B: TAF/FTC 25/200 mg QD coadministered with GSK3640254 200 mg QD on Days 1 through 7 (Period 2)

There is no washout between the last dose of study intervention (Treatment A) in Period 1 and initiation of study intervention (Treatment B) in Period 2. The participants will fast overnight for at least 8 hours prior to dosing and will receive a moderate fat meal 30 minutes prior to dosing. Participants will eat this meal in 30 minutes or less. Dose administration will occur within 5 minutes of completion of meal consumption.

Pharmacokinetic blood samples for analysis of TAF, FTC, and TFV will be collected before dosing (0 hour) on Days 2 through 14 (Period 1) and Days 1 through 7 (Period 2) and up to 24 hours after TAF/FTC dosing on Period 1, Day 14 and Period 2, Day 7. Pharmacokinetic blood samples for analysis of GSK3640254 will be collected before dosing (0 hour) on Days 2 through 7 (Period 2) and up to 24 hours after GSK3640254 dosing on Day 7.

Safety and tolerability will be assessed by monitoring and recording of AEs, clinical laboratory test results, vital sign measurements, 12-lead ECG results, and physical examination findings.

Study assessments will be performed as indicated in the Schedule of Activities (SoA) (Section 1.3). Participants will be confined to the clinic from Day –1 until discharge on Period 2, Day 10.

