# 8.3.1. Time Period and Frequency for Collecting AE and SAE Information

- All SAEs will be collected from the signing of the ICF until the end of the study at the time points specified in the SoA (Section 1.3).
- All AEs will be collected from the start of intervention until the end of the study at the time points specified in the SoA (Section 1.3).
- Medical occurrences that begin before the start of study intervention but after obtaining informed consent will be recorded on the Medical History/Current Medical Conditions section of the CRF, not the AE section.
- All SAEs will be recorded and reported to the sponsor or designee immediately and under no circumstance should this exceed 24 hours, as indicated in Appendix 6. The investigator will submit any updated SAE data to the sponsor within 24 hours of it being available.
- Investigators are not obligated to actively seek AEs or SAEs after the conclusion of the study participation. However, if the investigator learns of any SAE, including a death, at any time after a participant has been discharged from the study, and he/she considers the event to be reasonably related to the study intervention or study participation, the investigator must promptly notify the sponsor.

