# 5. CONSIDERATIONS FOR DATA ANALYSES AND DATA HANDLING CONVENTIONS

## 5.1. Study Treatment & Sub-group Display Descriptors

Treatment Group Descriptions									
Data Displays for Reporting									
Description Code Order in TLF									
TAF/FTC 25/200 mg QD on Days 1 through 14 in Period 1	TAF/FTC	1							
TAF/FTC 25/200 mg QD + GSK3640254 200 mg QD on Days 1 through 7 in Period 2	TAF/FTC+GSK3640254	2							

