## 10.2.2. Treatment Emergent Flag for Adverse Events

Flag	Definition
Treatment Emergent	
 
If AE onset date and time is on or after treatment start date and time & on or before treatment stop date and time + 4 days.
 
Study Treatment Start Date and Time ≤ AE Start Date and Time ≤ Study Treatment Stop Date and Time + 4 days.
 
If the AE onset date is completely missing, the AE is considered as treatment emergent.
 

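### The AE tables give counts and percentages for about 14 days on TAF/FTC alone and about 9 days on the combination, with no adjustment for time at risk

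*SAP*

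**What the plan says.** The first secondary objective (Protocol Section 3) covers the safety and tolerability of TAF/FTC given alone and when "coadministered with GSK3640254 in healthy participants".

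SAP Section 5.1 defines two treatment groups for displays, in this order:
- "TAF/FTC 25/200 mg QD on Days 1 through 14 in Period 1"
- "TAF/FTC 25/200 mg QD + GSK3640254 200 mg QD on Days 1 through 7 in Period 2"

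Protocol Section 4.1 states: "There is no washout between the last dose of study intervention (Treatment A) in Period 1" and the start of Period 2. Confinement runs "until discharge on Period 2, Day 10".

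Protocol Section 8.3.1 states: "All AEs will be collected from the start of intervention until the end of the study". In the Schedule of Activities, AE review runs to Period 2 Day 10. SAP Section 10.2.2 flags an event as treatment-emergent if "Study Treatment Start Date and Time ≤ AE Start Date and Time ≤ Study Treatment Stop Date and Time + 4 days".

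SAP Section 10.9.5 lists AE Tables 2.1 to 2.6. The first is "Summary of Adverse Events by System Organ Class and Preferred Term". Tables 2.4 and 2.5 also count occurrences. The Programming Notes for all six are blank, and the general standard for categorical data in SAP Section 10.3.2 is counts and percentages. Neither document mentions person-time, an exposure-adjusted rate or the unequal period lengths in connection with AEs.

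**The concern.** The alone-versus-combination AE display is the main evidence for the first secondary objective. A participant is watched for about half as long again on TAF/FTC alone as on the combination. A longer window collects more events at the same daily risk, so equal percentages in the two columns would not mean equal rates. A reader who takes the percentages at face value could misjudge how tolerability changes when GSK3640254 is added.

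Two related rules are missing. The SAP does not say which treatment an AE belongs to around the switch from Period 1 to Period 2. It also does not state the denominator for the combination column if someone leaves during Period 1; withdrawn participants are not replaced (SAP Section 10.5.1).

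**Working it through.** **1. Check the day count against the protocol's own figure.** Screening 28 days + Period 1 14 days + Period 2 to Day 10 = 28 + 14 + 10 = 52 days. This matches the approximate duration in the Protocol synopsis.

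**2. Observation windows.**
- TAF/FTC alone: from the Period 1 Day 1 dose to the Period 2 Day 1 dose, with no gap. T1 = 14 elapsed days.
- Combination: from the Period 2 Day 1 dose to discharge on Day 10. T2 = 10 − 1 = 9 elapsed days, or 10 calendar days.
- The treatment-emergent limit is Day 7 + 4 days = Day 11. That is after discharge, so it does not extend T2.

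**3. Occurrences, at an equal and constant daily rate.** The shortfall is 1 − T2/T1.
- 9 elapsed days: 1 − 9/14 = 35.7%.
- 10 calendar days: 1 − 10/14 = 28.6%.
- Equal occurrence counts would need a combination rate of 14/9 = 1.56 times the TAF/FTC-alone rate.

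**4. Participants with at least one event.** Let p1 be the incidence over 14 days. Then p2 = 1 − (1 − p1)^(T2/T1), and the shortfall is 1 − p2/p1. The documents give no AE rate for TAF/FTC alone, so p1 is an assumption, shown over a range.

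| p1 (assumed) | p2, 9 days | shortfall | p2, 10 days | shortfall |
|---|---|---|---|---|
| 5% | 3.2% | 35.1% | 3.6% | 28.0% |
| 10% | 6.5% | 34.5% | 7.2% | 27.5% |
| 30% | 20.5% | 31.7% | 22.5% | 25.0% |
| 50% | 36.0% | 28.1% | 39.0% | 21.9% |
| 90% | 77.2% | 14.2% | 80.7% | 10.3% |

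With 16 participants and p1 = 50%, the expected numbers affected are 16 × 0.50 = 8.0 and 16 × 0.360 = 5.8, at identical daily risk.

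**5. What a per-day rate does.** If all 16 complete, the denominators are 16 × 14 = 224 and 16 × 9 = 144 participant-days. At an illustrative 0.05 occurrences per day, the expected counts are 11.2 and 7.2, a ratio of 0.64. Divided by participant-days, both are 5.0 per 100.

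**6. Attribution at the switch.** If the 4-day extension were applied to each treatment separately, the TAF/FTC-alone window would run 13 + 4 = 17 elapsed days from first dose. It would overlap the combination window by 17 − 14 = 3 days, and the occurrence shortfall would be 1 − 9/17 = 47%. The SAP does not say whether the rule applies per treatment or to the whole study.

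**The case against.** **Layout.** The AE titles do not say that results are by treatment, whereas the PK table titles do, and the shells are held in the sponsor's standards. This stands as a caveat. Two columns are nevertheless the likely reading: SAP Section 5.1 gives the treatments a display order, and SAP Section 10.3.2 reports data by actual treatment received.

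**Descriptive, small and disclosed.** Protocol Section 9.4.2 plans no formal safety analysis and about 16 participants are treated. The group descriptions state the dosing days, and exposure and AE listings are planned. All of this is true, and it limits the point to an improvement in presentation. Chance variation is also larger than the effect. With 11.2 and 7.2 expected occurrences, treated as independent Poisson counts, the standard error of the log rate ratio is √(1/11.2 + 1/7.2) = 0.48. That is a 95% factor of exp(1.96 × 0.48), about 2.6 either way.

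**Direction.** A reader might infer that the tables are biased towards the combination looking safer. The documents do not support that, because ascertainment per day is not equal:
- ECGs: Day 1 only in Period 1 (1/14 = 0.07 per day), against Days 1, 4, 7 and 9 in Period 2 (4/9 = 0.44).
- Laboratory tests after first dose: Days 7 and 14 (2/14 = 0.14), against Days 3, 7 and 9 (3/9 = 0.33).
- On-study C-SSRS: Period 2 only.

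Clinically significant test abnormalities count as AEs (Protocol Appendix 6). Contact dermatitis, attributed mainly to ECG electrodes in the single-dose part, was also among the most frequent AEs in Study 207187. If daily ascertainment were 1.56 times higher in Period 2, the time-at-risk gap would be cancelled. This objection stands in full.

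**Conclusion.** The AE summaries for the two treatments rest on about 14 and about 9 elapsed days, and the plan does not adjust for it. Assuming constant and equal daily risk, equal ascertainment and full follow-up, the combination would show about 36% fewer occurrences. It would show about 14% to 35% fewer affected participants as assumed 14-day incidence falls from 90% to 5%. On 10 calendar days these become about 29% and about 10% to 28%.

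Two stronger readings should be avoided. The shortfall is not a fixed percentage, because it depends on an incidence that the documents do not give. Nor should it be called a halving on the basis of 7 against 14 dosing days, because AE collection continues after the last combination dose. The net direction remains open given the monitoring differences. No inferential result is affected; this is a low-cost improvement to the display for a secondary objective.

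**What to change.** In SAP Tables 2.1, 2.2 and 2.6, add by treatment:
- AE occurrences per 100 participant-days;
- participants with a first event per 100 participant-days at risk, with time at risk ending at that first event;
- as denominator, the participants who took at least one dose of that treatment;
- a rule assigning each AE to the treatment being taken at onset, with Period 1 ending at the first Period 2 dose;
- a footnote giving the two observation lengths.

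A matched-window table (such as Period 1 Days 8–14 against Period 2 Days 1–7) is not recommended. It would discard Period 2 Days 8–10, which fall within the treatment-emergent limit.

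The cost is SAP wording and one or two extra columns, using onset and dosing times already collected. The rates will be imprecise with about 16 participants. They will not remove the difference in monitoring density or the confounding of treatment with period in a fixed-sequence design, and the report should say so.

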### 5.2. Baseline Definitions

For all endpoints (except as noted in baseline definitions), the baseline value will be the latest pre-dose assessment with a non-missing value, including those from unscheduled visits. If time is not collected, Day 1 assessments are assumed to be taken prior to first dose and used as baseline. Baseline is applied to each treatment period.

Parameter	Study As	sessment Basel	s Considered as ine	Baseline Used in Data Display					
	Screening	Day -1	Day 1 (Pre-Dose)	Period 1 Period 2					
Safety									
Vital Sign	Х	Х	X	Day 1 (Pre-Dose) for each period					
12-Lead ECG	Х	Χ	Х	Day 1 (Pre-Dose)[1] for each period					
Hematology	Х	Х		Day -1 Period 1 Day 14					
Clinical Chemistry	Х	Х		Day -1 Period 1 Day 14					
Urinalysis	Х	Χ		Day -1	Period 1 Day 14				

 The average (for quantitative assessments) or the worst case (for interpretation) of the predose triplicate assessments on Day 1 of Period 1 will be used as the baseline for Period 1. The average (for quantitative assessments) or the worst case (for interpretation) of the predose triplicate assessments on Day 1 of Period 2 will be used as the baseline for Period 2.

Unless otherwise stated, if baseline data is missing no derivation will be performed and baseline will be set to missing.

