## **Time and Events Table**

Period 1			Period 2								р	Notes			
Procedure	Day –1	Day 1-5	Day 6-13	Day 14	Day 1	Day 2	Day 3	Day 4	Day 5	Day 6	Day 7	Day 8	Day 9 	Day 10	
Admit to clinic	Х														
Discharge from clinic														Х	
Brief physical examination	X												Х		A brief physical examination will include, at a minimum, assessments of the skin, lungs, cardiovascular system, and abdomen (liver and spleen).
Vital sign measurements	Χ	Χ	D7		Χ			Χ			Х		Χ	Х	
Single 12-lead ECG	Х	D1			X			X			X		X		All ECGs in Period 1 and 2 will be pre-dose, post-dose at 2 hours, and post-dose 4 hours. The predose ECGs on Day 1 of both Period 1 and Period 2 will be taken in triplicate.
Drug, alcohol, and cotinine screen	Х														See Protocol Appendix 2 for specific tests to be performed.
Laboratory assessments (hematology, chemistry, urinalysis)	Х		D7	Х			Х				Х		Х		See Protocol Appendix 2 for specific tests to be performed.
Pregnancy test	Χ												Χ		
Columbia-Suicide Severity Rating Scale					Х						Х				

	Period 1			Period 2								p	Notes		
Procedure	Day -1	Day 1-5	Day 6-13	Day 14	Day 1	Day 2	Day 3	Day 4	Day 5	Day 6	Day 7	Day 8	Day 9 	Day 10	
Genetic sample (Optional)	Х														
Study intervention: TAF/FTC 25/200 mg		Х	Х	Х	Х	Х	Х	Х	Х	Х	Х				
Study intervention: GSK3640254 200 mg					Х	Х	Х	Х	Х	Х	Х				
TAF, FTC, and TFV serial PK sampling				х	х						х	Х			Blood collection for PK analysis of TAF, FTC, and TFV will be collected at 0.25, 0.5, 0.75, 1, 1.5, 2, 3, 4, 5, 6, 8, 12, and 24 hours postdose (Period 1, Day 14 and Period 2, Day 7).
TAF, FTC, and TFV trough PK sampling		D2-5	Х	Х	Х	Х	Х	Х	Х	Х	Х				Blood collection for TAF, FTC, and TFV trough PK samples will be collected on Period 1, Days 2 through 14 and Period 2, Days 1 through 7.
GSK3640254 serial PK sampling											Х	Х			Blood collection for PK analysis of GSK3640254 will be collected at 1, 2, 2.5, 3, 3.5, 4, 4.5, 5, 6, 8, 12, and 24 hours postdose (Period 2, Day 7).

	Period 1			Period 2							Follow-up			Notes	
Procedure	Day –1	Day 1-5	Day 6-13	Day 14	Day 1	Day 2	Day 3	Day 4	Day 5	Day 6	Day 7	Day 8	Day 91	Day 10	
GSK3640254 trough PK sampling						Х	Х	Х	Х	Х	Х				Blood collection for GSK3640254 trough PK samples will be collected on Period 2, Days 2 through 7.
AE review		←======→													
SAE review	←														
Concomitant medication review	+	=====			======	=====	======	=====	=====	=====	=====	=====	======	==->	

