#### 10.3.2. Reporting Standards

#### General

- The current GSK Integrated Data Standards Library (IDSL) will be applied for reporting, unless otherwise stated (IDSL Standards Location: https://spope.gsk.com/sites/IDSLLibrary/SitePages/Home.aspx):
  - 4.03 to 4.23: General Principles
  - 5.01 to 5.08: Principles Related to Data Listings
  - 6.01 to 6.11: Principles Related to Summary Tables
  - 7.01 to 7.13: Principles Related to Graphics
- Do not include participant level listings in the main body of the GSK Clinical Study Report. All participant level listings should be located in the modular appendices as ICH or non-ICH listings.

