#### **Formats**

- All data will be reported according to the actual treatment the participant received unless otherwise stated.
- GSK IDSL Statistical Principles (5.03 & 6.06.3) for decimal places (DP's) will be adopted for reporting of data based on the raw data collected, unless otherwise stated.
- Numeric data will be reported at the precision collected on the eCRF.
- The reported precision from non eCRF sources will follow the IDSL statistical principles but may be adjusted to a clinically interpretable number of DP's.

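### Are the QTc maxima in SAP Tables 2.16 and 2.17 misleading because TAF/FTC alone has 2 scheduled post-baseline ECGs and the combination has 9?

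*SAP*

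**What the plan says.** SAP 10.9.5 lists two categorical QTc tables: Table 2.16, "Summary of Maximum QTc Values Post-Baseline Relative to Baseline by Category", and Table 2.17, "Summary of Maximum Increase in QTc Values Post-Baseline Relative to Baseline by Category". They use the standard shells EG10 and EG11. Neither title mentions treatment, and the programming notes are blank. Under SAP 10.3.2, "The current GSK Integrated Data Standards Library (IDSL) will be applied for reporting, unless otherwise stated". SAP 10.9.2 adds that "Non-Standard displays are indicated in the 'IDSL / Example Shell' or 'Programming Notes' column", so a blank note means the library shell is used as it stands.

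The ECG row of the Time and Events Table (SAP 10.1.1, same as protocol 1.3) marks Day -1, Period 1 Day 1, Period 2 Days 1, 4 and 7, and follow-up Day 9. Its note reads "All ECGs in Period 1 and 2 will be pre-dose, post-dose at 2 hours, and post-dose 4 hours". SAP 5.2 says "Baseline is applied to each treatment period", and for ECGs that baseline is the Day 1 pre-dose triplicate of the period concerned.

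Treatment columns can be inferred. SAP 5.1 defines two ordered display groups, the first being "TAF/FTC 25/200 mg QD on Days 1 through 14 in Period 1", and SAP 10.3.2 states "All data will be reported according to the actual treatment the participant received unless otherwise stated".

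**The concern.** A maximum grows with the number of readings behind it. If the two tables carry a TAF/FTC column and a combination column, the second draws on more than four times as many scheduled ECGs as the first, and it is the column that contains GSK3640254. Protocol 2.3 names QTc prolongation among that drug's major risks, and ECG safety with and without it is a secondary objective (protocol 3). A reader who sets the columns side by side could credit GSK3640254 with category shifts that come partly from more frequent measurement. The SAP text does not restrict the maximum to matched time points and does not mention the imbalance.

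**Working it through.** The plan states no ECG count per treatment and no precision for QTc, so there is no figure of its own to reproduce.

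**1. Scheduled post-baseline ECGs.** Each period's Day 1 pre-dose triplicate is that period's baseline and drops out.
- TAF/FTC: Day 1 at 2 h and 4 h = 2.
- Combination: Day 1 (2) + Day 4 (3) + Day 7 (3) + Day 9 (1) = 9, or 8 without Day 9.

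Day 9 lies inside the on-treatment window of treatment stop plus 4 days (SAP 10.2.1). Counting it as one ECG is a reading: no dose is given that day, so the pre-dose and post-dose times do not apply. Unscheduled ECGs enter worst-case values (SAP 10.3.2), and participants who stop early have the Day 9 evaluations, so individual counts can differ.

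**2. Expected maximum with no drug effect.** For k independent normal readings, E[max_k] = ∫ x·k·φ(x)·Φ(x)^(k−1) dx, in SD units. This gives 0.564 (k = 2), 1.424 (k = 8) and 1.485 (k = 9). With within-period correlation ρ, the gap is √(1−ρ) × (E[max_k] − E[max_2]).
- 9 versus 2: 1.485 − 0.564 = 0.921 at ρ = 0; × √0.5 = 0.651 at ρ = 0.5.
- 8 versus 2: 0.859 and 0.608.

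The documents give no within-participant SD. For an assumed 6 to 12 msec, 9 versus 2 is 5.5 to 11 msec at ρ = 0 and 3.9 to 7.8 msec at ρ = 0.5.

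**3. Maximum above 450 msec.** SAP 10.7.1 lists this limit but does not tie it to these tables. For a participant with true QTcF μ and independent readings, P = 1 − Φ((450 − μ)/SD)^k. At μ = 430 and SD 10: Φ(2) = 0.97725, so 1 − 0.97725² = 4.5% and 1 − 0.97725⁹ = 18.7%.

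| μ (msec) | SD (msec) | 2 vs 9 ECGs, ρ = 0 | 2 vs 9 ECGs, ρ = 0.5 |
|---|---|---|---|
| 430 | 6 | 0.09% vs 0.39% | 0.08% vs 0.34% |
| 430 | 8 | 1.24% vs 5.45% | 1.18% vs 4.07% |
| 430 | 10 | 4.50% vs 18.7% | 4.15% vs 12.5% |
| 430 | 12 | 9.33% vs 35.6% | 8.41% vs 22.6% |
| 420 | 10 | 0.27% vs 1.21% | 0.26% vs 1.01% |
| 410 | 10 | 0.006% vs 0.029% | 0.006% vs 0.027% |

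All three values of μ pass the screening ECG criterion (protocol 5.2, criterion 23). The gap is material only near the limit and with a fairly large SD. The documents give no QTcF distribution, so an expected number of affected participants cannot be computed.

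**4. Increase above 60 msec.** This is the only increase limit in the SAP (10.7.1). With a triplicate baseline (noise SD/√3), SD 12 and independent readings, the chance that at least one of 16 participants crosses it, 1 − (1 − p)^16, is 0.024% versus 0.107%. If averaging the triplicate removed no noise, simulation gives p = 0.039% versus 0.162% per participant, so 1 − (1 − 0.00039)^16 = 0.6% versus 1 − (1 − 0.00162)^16 = 2.6% per trial. The category is very unlikely to be populated by the imbalance alone.

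**The case for a change.** The case for a change is that treatment columns are the natural reading of SAP 5.1, 5.2 and 10.3.2, that the direction of the bias does not depend on the assumed SD or correlation, and that a footnote with ECG counts would cost almost nothing. The unseen shells may also use a lower increase category. At 30 msec, a limit not in the documents, the no-effect chance per participant is 0.9% versus 3.8% at SD 10 and 3.0% versus 11.2% at SD 12 (triplicate baseline, independent readings), though about zero at SD 5.

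The counts and the direction stand. The defect itself is not shown. The complaint needs tables with treatment columns, no visit rows and no note, and none of these can be read from the documents. Figure 2.1 and the PK summary tables name treatment in their titles, while 2.16 and 2.17 do not. SAP 10.4.1 refers to a row pooling all post-baseline visits in related safety summaries, so visit rows may already be standard.

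The remedy would not deliver a fair comparison either. The only post-baseline time points scheduled in both periods are Day 1 at 2 h and 4 h. Rows for these would equalise the counts but cover only the first GSK3640254 dose, whereas repeat-dose Cmax was 1.9- to 2.3-fold that of Day 1 (protocol 2.2.2). They would also set change from a drug-free baseline beside change from a baseline taken after 14 days of TAF/FTC. The heavier ECG schedule in Period 2 follows the drug with the named QTc risk, which is a fair use of a worst-case table.

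**Conclusion.** No change is needed. If the tables are split by treatment, the maxima do rest on 2 and 9 scheduled ECGs and are not comparable as they stand. With no drug effect the combination maximum is expected to be higher by 0.65 to 0.92 SD, on an assumed correlation of 0.5 to 0. But the tables are a descriptive worst-case screen, protocol 9.4.2 plans no formal safety analysis, and no text in the plan compares the maxima. The imbalance can inflate an apparent GSK3640254 effect but cannot conceal one. Anyone who sees a shift in Table 2.16 or 2.17 can check it against Table 2.15, against Figure 2.1 (mean QTcF change with 95% CI by time point and treatment) and against Listing 28 (every ECG value). The ECG schedule that explains the shift is reprinted in the SAP. A note of the ECG counts under the two tables would be a harmless reporting courtesy, but it would alter no result or conclusion. The msec figures and probabilities rest on an assumed SD of 6 to 12 msec and normal readings; the counts do not.
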